5. Study Methods

- (1) This study uses a multicenter, randomized, single-blind, parallel-controlled method to observe the efficacy and safety of the MicroHand S endoscopic instrument control system in clinical application.
- (2) The subjects' vital signs are recorded before the start of this study, which include blood routine, liver and kidney function, electrolytes, coagulation function, electrocardiogram, urine/blood pregnancy test (female) and related imaging examination. Preoperative combined medications are also recorded.
- (3) Qualified subjects are divided into the experimental group and the control group by randomized number given in an envelope. Both the endoscopic instrument control systems in two groups are examined before the test. After anesthesia, the endoscopic instrument control system is placed in an appropriate position. Then we connect the wires and power up the system. According to the requirements of the surgery, the operative arms are placed and slowly pushed through the Trocars of the abdominal wall. The surgeons start to perform the operation.
- (4) Surgical success rate, intraoperative blood loss, operative time, and installation time are recorded, as well as whether adjacent organs and blood vessels are injured due to the malfunction of the test system. The breakage rate of gallbladders is calculated. Surgeons need to fill the satisfaction questionnaire after the surgery.
- (5) Subjects take a test in 24 ± 2 hours after surgery using visual analogue scale (VAS) to evaluate the pain score. Postoperative blood routine examination, liver and kidney function, and electrolyte examination are performed. Time to first flatus, postoperative complications and hospital stay are recorded. Postoperative combined medications are also recorded. Adverse events and severe adverse events are assessed separately in 30 ± 5 days after surgery.
- (6) After the follow-ups of all subjects, the data will be arranged for statistical analysis. Ultimately the data of the two groups will be compared, so as to prove whether the experimental product developed by WEGO Surgical Robot Co., Ltd is non-inferior to the control group.

6. Arms and Interventions

- (1) Experimental group: MicroHand S endoscopic instrument control system
Using the MicroHand S endoscopic instrument control system to treat gallstone or cholecystitis in minimal invasive surgery.

(2) Control group: da Vinci endoscopic instrument control system

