The breakage rate of gallbladder is defined as the proportion of the subjects in the experimental group or the control group with specimen breakage.

(2) Comprehensive Complication Index (CCI)

CCI is calculated using online tools provided by <http://cci.assessurgery.com>. Based on the Clavien-Dindo complications grade system (appendix.1), all complications and adverse events after surgical intervention are taken into consideration. The overall incidence is measured on a scale ranging from 0 (no complication) to 100 (death).

(3) Operative time (min)

The length of time from the beginning of the operation after the robot installation to the end of the suture of the incision.

(4) Intraoperative bleeding (L)

The total bleeding volume from the beginning of the operation to the end of the suture of the incision. It can be calculated by measuring the blood volume in the vacuum suction device and weighing the gauze after using them to wipe the bleeding.

(5) Postoperative pain

Postoperative pain is assessed by visual analogue scale (VAS) 24-26 hours after the operation, ranging from 0 (no pain) to 10 (maximum pain).

(6) Time to first flatus (h)

The time from the end of the operation to the subject's first flatus after surgery.

(7) Surgeon's satisfaction

After the operation, surgeons fill a questionnaire to score the flexibility, intuition and stability of the products, as well as their sense of delay and fatigue when using the products. Each question in the score ranges from 1 to 5 points and the total score is 100.

(8) Installation time (min)

The time from the power-on of the products to the end of the connection between trocars and the operative arms.

(9) Hospital stay (days)

The total hospital days of subjects from admission to discharge.

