8.3 Selection criteria of surgeons

In order to strictly guarantee the homogeneity of the surgeons, they need to meet a certain standard. Generally, they are required to have more than 5 years of endoscopic surgery experience and more than 1 year of robotic surgery experience, and have passed the test product training and obtained the operation training certification.

9. Safety evaluation

9.1 Safety evaluation indicators:

- (1) The incidence of organ and vascular injury events which include the following:
 - 1) Any damage to the adjacent organs (liver, spleen and intestine) due to the malfunction of the products.
 - 2) The blood vessel injury caused by the malfunction of the products during the operation resulting in massive bleeding.
- (2) The incidence of adverse events from the end of the operation to discharge.
- (3) The incidence of the malfunction of the products which includes the following:
 - 1) The connection between the console and the operative arms receives strong interference, which cannot be solved by resetting.
 - 2) The tissue cannot be loosened when the surgical instrument is clamped.
 - 3) Device installation false alarm.
 - 4) Failure or damage of the surgical instruments during an operation.
- (4) Vital signs: temperature, heart rate, respiration, and mean arterial pressure.
- (5) Laboratory examinations: blood routine, liver and kidney function, and electrolytes.

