9.2 Indicators measurement methods

- (1) Vital signs: Twice a day before surgery, twice at the beginning and end of the operation, and twice at 3-5 days after the operation. Six times in total.
- (2) Laboratory examination: once before the operation and once within 3~5 days after the operation. At least twice in total.

10. Procedures

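### The adverse-event rate in section 9.1(2) opens only when the operation ends, so an intraoperative event without malfunction that is resolved by closure, without conversion, enters no safety incidence.

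*Protocol*

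**What the plan says.** Section 9.1 of the protocol lists five safety indicators.

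- 9.1(1), organ and vascular injury, has two parts: "Any damage to the adjacent organs (liver, spleen and intestine) due to the malfunction of the products" and "The blood vessel injury caused by the malfunction of the products during the operation resulting in massive bleeding".
- 9.1(2), adverse events: "The incidence of adverse events from the end of the operation to discharge".
- 9.1(3), malfunctions, lists device faults, for example "Failure or damage of the surgical instruments during an operation".
- 9.1(4), vital signs, are timed in section 9.2: "Twice a day before surgery, twice at the beginning and end of the operation, and twice at 3-5 days after the operation".
- 9.1(5), laboratory tests, are also timed in 9.2: "once before the operation and once within 3~5 days after the operation".

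The data-collection text in section 5(4) carries the same restriction as 9.1(1). What is recorded is "whether adjacent organs and blood vessels are injured due to the malfunction of the test system". The Comprehensive Complication Index (CCI), a secondary efficacy outcome in section 8.2(2), is described by "all complications and adverse events after surgical intervention are taken into consideration".

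Section 8.1 recognises that organ injury and uncontrolled bleeding can happen during surgery for reasons other than malfunction. It places them under passive conversion, ascribes them to surgical technique, and lists malfunction as a separate category.

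**The concern.** In this trial the device acts on the patient during the operation. By the step list in section 10.2, the products are switched off at about the time of wound closure, which is when the window in 9.1(2) opens. The only general adverse-event rate in the protocol thus leaves out the period of device exposure. The injury indicator that does cover that period depends on a judgement that a malfunction was the cause.

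That condition is narrower than the aim in section 1, which speaks of injury related to the test product. Injury can be related to a device that is working as designed, for instance through its handling, view or instrument control. The condition also rests on a blurred boundary. Section 8.1 lists improper handling of the arms among the causes of malfunction, yet puts technique-related accidents under passive conversion. The surgeons, who are best placed to judge the cause, operate the console and so know which system they are using. A rate that counts events whatever their cause would not depend on that judgement.

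At stake is whether the safety comparison can show a difference in harm that arises and is dealt with inside the operation.

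**Working it through.** The protocol states no figure on this point, so the check is mainly one of reading. Take a test case: during dissection, with the system working normally, the surgeon injures a vessel or organ, repairs it with the robot, completes the operation robotically, and the patient has no later consequence. Each place that might count it is set out below.

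| Place | Condition for counting | Test case counted? |
|---|---|---|
| 9.1(1) | Malfunction as cause; for vessels, massive bleeding as well | No, by cause |
| 9.1(2) | Falls between end of operation and discharge | No, by time |
| 9.1(3) | Device fault | No, not a device fault |
| 9.1(4) with 9.2 | Vital signs at start and end of surgery | Not as an event; a lasting effect might show in the end reading |
| 9.1(5) with 9.2 | Laboratory tests before and 3-5 days after surgery | Not as an event |
| 5(4) | Injury due to malfunction | No, by cause |
| 5(5) and 7.5 | AE assessment at 30 ± 5 days; safety evaluated at end of follow-up | Neither states when counting opens |
| 8.1 | Failure through passive conversion or malfunction | No; completed robotically, so a success |
| 8.2(2), CCI | After the intervention | No, by time |
| 8.2(4), blood loss | Volume over the operation | Contributes volume only; efficacy outcome |
| 8.2(1), breakage | Broken gallbladder specimen | Only if the specimen is broken; efficacy outcome |

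The test case enters no event-incidence safety indicator.

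Three variations show where the gap ends:

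1. If the injury forces conversion, it is a passive conversion and so a failure in the primary outcome. It is then counted, but as efficacy.
2. If it leads to something that persists or appears after surgery, that consequence can enter 9.1(2) and the CCI.
3. If a malfunction caused it, 9.1(1) applies, but only within its wording. A vessel injury without massive bleeding does not meet it. Nor does an injury to a structure outside the three named organs, such as the bile duct, if that list is read as complete.

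**Size.** The number per arm is 84 (section 7.6). The proportion of subjects with such an event is not in the documents. Assuming 2% to 10%:

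- 0.02 × 84 = 1.7, about 2 subjects per arm
- 0.10 × 84 = 8.4, about 8 subjects per arm

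This is an upper bound for the assumed range. It treats every such event as uncounted and subtracts none that variations 1 and 2 would capture.

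**The case against.** The strongest reply is that the trial is not blind to intraoperative harm. Injury or bleeding that forces conversion is a failure in the primary outcome with no malfunction needed. Blood volume and gallbladder breakage are compared between arms without any malfunction condition. Vital signs are a safety indicator taken at the start and end of surgery. Section 9.1(2) does not say that onset must be after the operation, so an event still present at closure could be counted. All of this stands, and it confines the gap to events that are resolved by closure without conversion. It does not remove the gap: the efficacy outcomes are not safety incidences, and two vital-sign readings can miss a transient event.

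A reader might infer more than the text supports, in three ways:

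- *That every intraoperative adverse event is lost.* Variations 1 and 2 in the working show otherwise.
- *That intraoperative events go unrecorded.* Section 5(5) provides for AE and SAE assessment without stating an opening time. Section 7.7 requires any AE-related drop-out to be entered in the CRF and notified to the sponsor, whatever its relation to the product. What the text fixes is the reported rate; it does not show that the events are never written down.
- *That the arms are most likely to differ in this period.* The documents give no evidence of that. Both arms have robotic surgery, and events of pneumoperitoneum or anaesthesia are common to both.

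It could also be said that the statistical analysis plan may settle the window. But the protocol has not left it open: 9.1(2) states both its start and its end.

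**Conclusion.** The point holds in a limited form. As written, section 9.1(2) leaves the period of device use out of the general adverse-event rate, and the malfunction condition in 9.1(1) and 5(4) does not fill the space. What is uncounted is the intraoperative adverse event without malfunction, without conversion and without postoperative consequence. Section 8.1 shows that the protocol itself expects accidents of this type.

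The number of such events cannot be derived from the documents. The figure of at most about 2-8 of 84 per arm rests wholly on the assumed 2-10%. The gap in definition does not depend on it.

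The primary outcome, its analysis and the sample size are not affected. The reason to act is that the safety comparison would otherwise have no event rate for part of the time the device is in use. If the case form does not capture onset as events happen, the information may not be recoverable later.

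**What to change.** Reword 9.1(2) so that the AE/SAE incidence opens at first trocar insertion in both arms and includes every event from then on, whether or not a malfunction is held responsible. Report events with intraoperative onset on a separate line from those with postoperative onset. Keep 9.1(1) as the malfunction-specific subset, and bring the injury recording in 5(4) into line so that injuries of any cause are captured.

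One fixed opening point is needed. First trocar insertion is preferable to the start of anaesthesia, which would add induction events that occur before either robot is connected. The price is that events before the first trocar stay outside the rate, equally in both arms.

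While 9.1(2) is being edited, its end at discharge should be reconciled with the 30 ± 5 day AE assessment in 5(5) and the 30-day safety follow-up in 7.5. That is a separate matter from when the window opens.

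The cost is the changed wording, one onset field on the AE form, and AE rates that will be slightly higher in both arms.

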9.2 Indicators measurement methods

- (1) Vital signs: Twice a day before surgery, twice at the beginning and end of the operation, and twice at 3-5 days after the operation. Six times in total.
- (2) Laboratory examination: once before the operation and once within 3~5 days after the operation. At least twice in total.

10. Procedures

10.1 Records needed before starting

- (1) Basic information of subjects: the gender, height, weight and vital signs, etc.
- (2) Medical history: course of disease, severity of illness, medication, and previous surgical history.
- (3) Informed consent form.
- (4) Electrocardiogram.
- (5) The imaging examination: color ultrasound of liver, bile, pancreas and spleen and electronic gastroscopy. For subjects who are more than 50 years old, heart ultrasound and neck vascular ultrasound are needed.
- (6) Laboratory examinations: blood routine, liver and kidney function, coagulation function and electrolytes.

10.2 Standard operating procedures

- (1) Examining the console: appearance inspection, instrument performance, screen display and technical index.
- (2) Examining the operative arms: appearance inspection, movements, instrument performance, and technical index.
- (3) Connecting the endoscopic instrument control system and preparing the initialization of the system for a few seconds.
- (4) Starting the operation: anesthesia, position adjustment, pneumoperitoneum, setting trocars, and 3D laparoscopic light source.
- (5) Brief procedures of the operation:
 - 1) The surgeons control the operative arms to grab the neck of the gallbladder or Hartmann's fossa with the bipolar electric knife and pull it to the upper right.
 - 2) The surgeons use the electric hook to dissociate the serosal membrane of gallbladder tube, make blunt dissection of gallbladder tube and gallbladder artery, and pay attention to distinguish common bile duct and common hepatic duct.
 - 3) The surgeons use hemo-lok clips to clamp the tube as close as possible to the neck of the gallbladder, and cut with surgical scissor between two hemo-lok clips.
 - 4) The surgeons clamp the neck of the gallbladder and pull upward. Simultaneously, we use ultrasonic knife to carefully detach along the gallbladder wall. The assistant should pull gently to hold the tension between the gallbladder and liver, which makes it easier to detach.
 - 5) After fully dissociation of the gallbladder, the surgeons take it out of the abdominal cavity through the 12mm trocar. Then we check if there is any bleeding or leakage before withdrawing orderly.
 - 6) The surgeons suture the surface wounds and turn down the products.
